Title page

The Utility of Gastro-laryngeal Tube during Transesophageal Echocardiography: Prospective Randomized Clinical Trial

[name] ([contact])

M.D. Department of Anesthesiology and Reanimation, Bezmialem Vakif University School of Medicine, Istanbul, Turkey. ORCID ID: 0000-0003-0231-3636

[name] ([contact])

Assist. [name]. Department of Anesthesiology and Reanimation, Bezmialem Vakif University School of Medicine, Istanbul, Turkey. ORCID ID: 0000-0003-0426-8525

[name] ([contact])

Assoc. [name]. Department of Cardiology, Bezmialem Vakif University School of Medicine, Istanbul, Turkey. ORCID ID: 0000-0003-3355-0925

[name] ([contact])

[name]. Department of Anesthesiology and Reanimation, Bezmialem Vakif University School of Medicine, Istanbul, Turkey. ORCID ID: 0000-0003-0582-8723

[name] ([contact])

Assoc. [name]. Department of Anesthesiology and Reanimation, Bezmialem Vakif University School of Medicine, Istanbul, Turkey. ORCID ID: 0000-0002-0155-1387

Address all correspondence to:

[name]. Department of Anesthesiology and Reanimation, Bezmialem Vakif University School of Medicine, Istanbul, Turkey

Mail: [contact]

[contact]

Study Protocol

After approval from the Ethics Committee of Bezmialem Vakif University School of Medicine, study was performed for 42 patients scheduled for TEE under sedation and analgesia or general anesthesia. Patients with American Society of Anesthesiology (ASA) physical status I-II and aged 20-75 years old were included in this study. ts who were under 20 to over 75 years old, an allergy to anesthetic drugs, emergent procedure, uncontrolled cerebrovascular disease, drug and alcohol addiction, performed oropharyngeal surgery were excluded, as were all patients who refused written informed consent.

Preoperative evaluations were performed on all patients a day before procedure. Age, gender, height, weight, and ASA physical status were recorded. On the day of procedure, patients were taken to the procedure room after premedication with 0.003 mg/kg IV midazolam (Dormicum, Deva Holding Cor., Istanbul, Turkey). Standard monitoring procedures were used, including heart rate (HR), noninvasive blood pressure, electrocardiogram, peripheral oxygen saturation (SpO2).

Forty two patients were randomly assigned to either the Group 1 (n=22, sedation and analgesia without any airway instrumentation) or Group 2 (n=20, airway control provided by GLT after inducing sedation and analgesia). Also, randomization (1:1) was based on a computer generated random numbers table, using MedCalc v. 16 statistical software for Windows (medcalc.com.tr). All patients received standard intervention procedures determined by the same team of cardiologists and an anesthesiologist with experience in TEE. Standard intervention procedure protocol was not change in any way.

All patients received preoperative midazolam (0.01-0.02 mg/kg) before being taken to the procedure room. For patients in Group 1, a standardized sedation and analgesia was administered by an experienced anesthesiologist. After administration of lidocaine (1 mg/kg) and atropine sulfate (0.01 mg/ kg), and also preoxygenation (100% 4 L/min O2 for 3 min), patients were induced with propofol (1-2 mg/kg) and fentanyl (1-2 mcg/kg) via intravenous (IV) route at doses calculated according to ideal body weight. Anesthesia was maintained with propofol infusion (4 mg/kg/h). Repetitive IV boluses of propofol (0.1 mg/kg) were administered, if necessary. Patients received oxygen (100%, 3 L/min) through a nasal cannula during sedation and analgesia.

For patients in Group 2, after administration of lidocaine (1 mg/kg) and atropine sulfate (0.01 mg/ kg), and also preoxygenation (100% 4 L/min O2 for 3 min), patients were induced with propofol (1-2 mg/kg) and fentanyl (1-2 mcg/kg). After induction of anesthesia, supraglottic airway device named GLT (VBM Medizintechnik GmbH, Sulz, Germany) was inserted (Figure 3). Patients were ventilated mechanically with a tidal volume of 6–8 mL/kg

based on ideal body weight and a frequency of 12–14 breaths/min using a Dräger Primus ventilator (Dräger AG, Lübeck, Germany) after inserting the GLT. Repetitive IV boluses of propofol (0.1 mg/kg) were administered, if necessary. Also, GLT was then removed at the end of TEE procedure.

The anesthesiologist was responsible for patient comfort, hemodynamic stability, immobility, adequate analgesia and airway management.

We hypothesized that GLT, allowing passage of the TEE probe and ensuring supraglottic airway control, would provide more advantages in terms of hemodynamic stabilization, complications related airway management, cardiologist and patient satisfactions when used in a clinical setting. To date, there has been no detailed prospective clinical study analyzing the performance of the GLT during TEE. The present study sought to address this gap by performing a prospective clinical study to analyze the performance of the GLT during TEE. Our primary outcome measures were safety of airway management, and cardiologist and patient satisfactions. Our study also recorded demographic characteristics, intraoperative and postoperative hemodynamics, level of hypoxemia, and duration of procedure as secondary outcome measures.

Statistical Analysis

Data were analyzed using the Statistical Package for the Social Sciences program (SPSS 22.0; IBM). The Shapiro Wilk normality test was used to test whether quantitative variables showed a normal distribution. Differences between variables in two groups with normal distribution were compared with the paired t-test. Continuous variables distributed abnormally were compared between the groups using a Mann–Whitney U test. Differences between variables within the same group at different times were tested with the Friedman test, and significant variables had pairwise comparisons performed with the Dunn test. Categorical variables were summarized using frequencies and percentages, and were compared between the groups using a chi-square test or Fisher's exact test. Descriptive statistics are given as mean, standard deviation, median, Q1 (1st quartile), Q3 (3rd quartile), frequency and percentage (%). Results were evaluated at a 95% confidence interval at a significance level of p < 0.05. Consent to conduct the study was obtained from Local Ethic Committee of Bezmialem Vakif University.

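### Age, height and weight are recorded before the procedure, but no between-group comparison uses them and demographics are listed as outcomes: a modest, conditional loss of efficiency, not of validity

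*Combined protocol and SAP*

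**What the plan says.** The Study Protocol section describes an evaluation the day before the procedure: "Age, gender, height, weight, and ASA physical status were recorded". These values precede treatment, so the airway device cannot affect them.

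On allocation, it says that "randomization (1:1) was based on a computer generated random numbers table". No stratification factor, blocking or minimisation is described. The group sizes are given as "Forty two patients were randomly assigned to either the Group 1 (n=22, sedation and analgesia without any airway instrumentation" and "Group 2 (n=20, airway control provided by GLT after inducing sedation and analgesia".

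The paragraph before Statistical Analysis states: "Our primary outcome measures were safety of airway management, and cardiologist and patient satisfactions". It continues: "Our study also recorded demographic characteristics, intraoperative and postoperative hemodynamics, level of hypoxemia, and duration of procedure as secondary outcome measures".

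The between-group tests in Statistical Analysis are a t-test (called paired), the Mann-Whitney U test, and chi-square or Fisher's exact test. No regression, analysis of covariance or stratified test is mentioned, even as a sensitivity analysis.

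On monitoring, the protocol says: "Standard monitoring procedures were used, including heart rate (HR), noninvasive blood pressure, electrocardiogram, peripheral oxygen saturation (SpO2". It does not say that a value before induction was written down.

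**The concern.** The plan collects pre-treatment variables and then gives them the wrong role. Listed as secondary outcome measures, they fall under the general testing rules and could receive between-arm p-values. If allocation was random, such a p-value can reflect only chance. Their statistical use is as covariates, and no model uses them.

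Two things are at stake in a trial of 42. First, if age or body size predicts an outcome, a chance imbalance carries into the unadjusted difference in that outcome. Second, any outcome variation that these variables explain stays in the error term. The trial can detect only large differences, so a gain in precision at no cost in data is worth considering. Whether there is a gain depends on how strongly the covariates predict the outcomes, which the documents do not say.

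**Working it through.** The plan gives no power, effect size or SD, so it has no figure of its own to reproduce beyond 22 + 20 = 42.

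**Inputs from the documents:** n1 = 22, n2 = 20, alpha 0.05. **Assumptions:** two-sided testing; a continuous outcome; R², the share of within-group outcome variance explained by the covariates, between 0 and 30%.

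**1. Chance imbalance.** The standard error of a standardised baseline difference is sqrt(1/22 + 1/20) = 0.309.
- P(|difference| > 0.25 SD): 0.25/0.309 = 0.81, two-sided probability 0.42.
- P(|difference| > 0.5 SD): 0.5/0.309 = 1.62, two-sided probability 0.11.
- At least one of two independent covariates beyond 0.5 SD: 1 − (1 − 0.106)² = 0.20.

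An imbalance of 0.5 SD shifts the unadjusted difference by 0.5 × r, where r is the covariate-outcome correlation. For assumed r of 0.1, 0.3 and 0.5 the shift is 0.05, 0.15 and 0.25 SD. Each is below one standard error (0.309 SD).

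**2. Unadjusted detectable difference.** From the noncentral t with 40 degrees of freedom and standard error 0.309, 80% power is reached at 0.887 SD.

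**3. Adjusted detectable difference.** With q covariates the degrees of freedom are 40 − q, and the standard error is 0.309 × sqrt[(1 − R²) × (1 + q/(42 − q − 3))]. The second factor is the expected cost of chance correlation between covariates and group. For age and BMI, q = 2 and that factor is 1 + 2/37 = 1.054.

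| Assumed R² | Standard error (SD) | Detectable at 80% power (SD) | Power at 0.887 SD |
|---|---|---|---|
| Unadjusted | 0.309 | 0.887 | 80% |
| 0 | 0.317 | 0.912 | 78% |
| 5% | 0.309 | 0.889 | 80% |
| 10% | 0.301 | 0.865 | 82% |
| 20% | 0.284 | 0.816 | 86% |
| 30% | 0.265 | 0.763 | 90% |

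Break-even is at R² of about 5%.

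**4. A third covariate** (a pre-induction value, if one exists). With q = 3, break-even rises to about 8%. At R² = 0 the detectable difference is 0.925 SD and power at 0.887 SD is 77%, a loss of about 3 points.

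**The case against.** The strongest reply is that nothing here is an error. Unadjusted tests are valid under randomisation, and their standard error already allows for chance imbalance. That stands. A reader might infer from the imbalance probabilities that the planned comparisons are biased or lose control of type I error; the documents do not support that.

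The benefit is also assumed. No correlation between age or body size and any outcome is given, and no baseline value is described for any primary outcome. Eligibility is narrow on ASA class ("Patients with American Society of Anesthesiology (ASA) physical status I-II and aged 20-75 years old were included in this study"), which limits what that variable can explain. This stands too, and is why the R² range has to start at zero.

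A reader might infer that adjustment is free, by multiplying 0.887 by sqrt(1 − R²) to get 0.84, 0.79 and 0.74 SD at 10%, 20% and 30%. Those figures omit the lost degrees of freedom and the cost of estimating covariates; with two covariates the values are 0.865, 0.816 and 0.763 SD.

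A reader might also infer that pre-induction heart rate, blood pressure and SpO2 are already in hand. The protocol says that monitoring was used, and the haemodynamics it lists as recorded are intraoperative and postoperative. The planned within-group comparison over time does not establish that one of the times came before induction.

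Finally, no measurement scale is given for satisfaction or for level of hypoxaemia. If either is categorical, the linear model and the SD-based figures do not apply to it. For airway safety analysed as yes/no events, the proposal changes nothing.

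These points shrink the gain without removing it. Two covariates break even at a low R², and the loss if they are useless is small.

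**Conclusion.** The point holds as one of efficiency and robustness. Pre-treatment age, height and weight are recorded, all listed between-group tests are unadjusted, and no stratification is described (an inference from silence). Listing demographic characteristics as outcome measures is a misclassification that needs no assumption to establish.

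The size is modest and conditional. One covariate is out of balance by more than 0.5 SD with probability 11%. With age and BMI in the model, the change in detectable difference runs from a loss of 0.025 SD (0.887 to 0.912) at R² = 0 to a gain of 0.124 SD (0.887 to 0.763) at R² = 30%. This rests on a continuous outcome, two-sided testing and an R² that the documents do not supply. The change is advisable; its absence does not invalidate the trial.

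**What to change.** - **Continuous outcomes** (haemodynamics, procedure duration, and level of hypoxaemia and satisfaction if measured on a scale): use a linear model with group, age and BMI computed from the recorded height and weight. Fit it on ranks if the outcome is skewed.
- **Haemodynamics and SpO2:** add the pre-induction value only if one was recorded, and state whether it was.
- **Unadjusted comparison:** report it beside the model, as an independent-samples test. The plan names a paired t-test, which cannot apply to two separate groups of 22 and 20.
- **Sparse yes/no complications:** leave unadjusted.
- **Demographics:** remove them from the secondary outcomes and present them in a descriptive baseline table without p-values.
- **Timing:** the text is written in the past tense. If the model is added after results are known, label it post hoc.

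The cost is a few lines in Statistical Analysis and no new data for age and BMI. If the covariates turn out to be uninformative, it is about 2 points of power with two covariates and about 3 with three.

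### A paired t-test is named for comparing two independent, unequal randomised groups (22 vs 20); it should be an independent-samples t-test on all 42 patients

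*Combined protocol and SAP*

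**What the plan says.** The Study Protocol section describes two separate sets of patients. It introduces the first arm with these words: "Forty two patients were randomly assigned to either the Group 1 (n=22, sedation and analgesia without any airway instrumentation". The second arm, made up of different patients, is given as "Group 2 (n=20, airway control provided by GLT after inducing sedation and analgesia". On allocation the section says only that "randomization (1:1) was based on a computer generated random numbers table". It mentions no matching, crossover or other pairing of patients.

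The Statistical Analysis section then gives three rules for quantitative variables:

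- Normal data, between groups: "Differences between variables in two groups with normal distribution were compared with the paired t-test".
- Non-normal data, between groups: "Continuous variables distributed abnormally were compared between the groups using a Mann–Whitney U test".
- Repeated measurements within a group: "Differences between variables within the same group at different times were tested with the Friedman test", followed by Dunn pairwise comparisons.

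No independent-samples t-test is named anywhere. On the threshold, the section says "Results were evaluated at a 95% confidence interval at a significance level of p < 0.05"; it does not say whether tests are one- or two-sided.

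**The concern.** A paired t-test analyses the differences within one-to-one pairs. Here each patient belongs to one arm only and has no counterpart in the other. The test would be wrong for this design even with 21 patients per arm. With 22 and 20 it also cannot use everyone.

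If it were carried out literally, someone would have to line the two arms up by row in the data file and leave at least two Group 1 patients without a partner. The standard error, p-value and confidence interval would then depend on an arbitrary ordering, and a second analyst with the same data in another order would get different answers.

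The rule covers every continuous between-group comparison that passes the Shapiro-Wilk check. The likely candidates are haemodynamic values, procedure duration, continuous demographics and perhaps level of hypoxaemia. Haemodynamic stability is part of the stated hypothesis, so this is more than a matter of baseline tables.

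**Working it through.** **Can the sentence be read another way?** Three readings were tried.

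1. *It means change within a patient.* The sentence refers to two groups, and within-group change has its own rule (Friedman, then Dunn). This reading fails.
2. *The groups are matched.* The Study Protocol section describes only random allocation. This reading fails.
3. *It is a naming slip.* The rule for non-normal data uses Mann-Whitney U, which is an independent-samples test, for the same comparison. The two rules therefore assume different designs, and the Mann-Whitney rule is the one that agrees with the randomisation. A slip is plausible, but the text does not show it.

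**Inputs.** n1 = 22 and n2 = 20 (Study Protocol; 22 + 20 = 42, as stated). Alpha is 0.05 (Statistical Analysis), taken here as two-sided. The documents give no sample-size calculation, effect size or SD, so there is no figure of the plan's own to reproduce. Differences are expressed in SD units and are assumptions. Data are taken as normal with equal SDs, and arbitrary pairs as uncorrelated.

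**Degrees of freedom and interval width.**

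- Independent (pooled): df = 22 + 20 − 2 = 40; critical t = 2.021; standard error = √(1/22 + 1/20) = 0.309 SD; half-width = 2.021 × 0.309 = 0.624 SD.
- Twenty arbitrary pairs: df = 20 − 1 = 19; critical t = 2.093; standard error = √(2/20) = 0.316 SD; half-width = 2.093 × 0.316 = 0.662 SD.
- Ratio: 0.662 / 0.624 = 1.06.

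**Power.** This uses the noncentral t distribution, with noncentrality equal to the difference divided by the standard error.

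| Assumed difference | Independent, df 40 | 20 arbitrary pairs, df 19 |
|---|---|---|
| 0.5 SD | 35.2% | 32.4% |
| 0.8 SD | 71.5% | 67.0% |
| 0.887 SD | 80.0% | 75.8% |
| 1.0 SD | 88.5% | 85.1% |

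The 0.887 SD row is simply the difference at which the independent test reaches 80% power. The paired version needs 0.934 SD.

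**Type I error.** In 100,000 simulated trials with no true difference, both the independent test and the arbitrarily paired test rejected in 5.1%. The two disagreed on significance in 2.9% of trials under the null and in 9.7% at 0.8 SD.

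**Dependence on row order.** Datasets were simulated, and the same data were re-paired at random many times.

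- Correct p between 0.03 and 0.05: about half of the pairings gave p < 0.05, and the central 95% of p-values ran from about 0.008 to 0.13.
- Correct p between 0.001 and 0.01: more than 99% of pairings stayed significant.
- Correct p between 0.2 and 0.5: at most about 0.5% of pairings became significant.

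**An extreme case.** If both arms happened to be sorted in the file by the outcome under test, type I error would be about 60% to 65%, depending on which two patients were dropped. Sorting makes the artificial pairs strongly correlated, so the standard error is far too small.

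**The case against.** The strongest reply is that this is a wording error and that no wrong analysis has been shown. The section is in the past tense, the next sentence uses an independent-samples test, and a paired routine given 22 and 20 values fails unless someone forces pairs. The authors may well have run the ordinary two-sample t-test. That is a fair caution: the documents do not establish that a paired test was run, and the lost patients and row-order dependence follow only if it was. But a reader cannot tell which test lies behind the results, and the text needs the same correction either way.

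The second reply concerns size, and most of it stands. Arbitrary pairing leaves the false-positive rate near 5%, costs about 3 to 5 points of power and widens the interval by about 6%. The instability of p-values matters mainly close to the 0.05 threshold. The 60% to 65% type I error needs a file sorted by the very outcome being tested; nothing in the documents suggests this, and one ordering could not in general sort every outcome at once. It marks an extreme and is not an expected effect.

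The third reply concerns reach. The plan says: "Our primary outcome measures were safety of airway management, and cardiologist and patient satisfactions". Airway events, if recorded as categories, go to chi-square or Fisher tests and are untouched. The satisfaction scale is not given; an ordinal or skewed score would go to Mann-Whitney. Oxygen saturation is bounded at 100% and may well fail the normality check. So no primary outcome is shown to be affected, though satisfaction could be.

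**Conclusion.** The concern holds. As written, the plan assigns a paired test to independent groups, contradicts its own rule for non-normal data, and cannot be carried out on the full randomised sample. Invalid here means that there are no pairs, that any result would depend on an arbitrary ordering, and that at least two randomised patients would be left out. It does not mean a routinely inflated false-positive rate.

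The average loss is modest, and all the figures rest on the normality, equal-SD and two-sided assumptions stated above. The stronger reason to correct the text is that results from the named method could not be reproduced without knowing the row order. The 22/20 split is compatible with simple 1:1 randomisation and is not itself an error. The correction must be made because the sentence governs every normally distributed between-group comparison.

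**What to change.** In the Statistical Analysis section, replace the paired t-test with an independent-samples t-test for between-group comparisons of normally distributed variables, using all 22 and 20 patients. Say which form is used: Welch is a sound default because it does not assume equal variances, though a pooled test named in advance would also fit the design. Report the mean difference with its 95% confidence interval for each comparison.

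Confirm from the SPSS output which test was run. If it was already the independent-samples test, only the wording changes. If it was the paired test, rerun those comparisons. State the scale of the satisfaction scores, so that the reader can see which rule applies to them.

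The cost is one phrase in the text and, at most, a rerun of the affected comparisons. No further data are needed.

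### Haemodynamic stabilisation (secondary outcome): the only analysis that uses time is within each arm, and no between-arm test is tied to a reading, change, baseline or stability measure

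*Combined protocol and SAP*

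**What the plan says.** The hypothesis, in the paragraph before Statistical Analysis, is that GLT "would provide more advantages in terms of hemodynamic stabilization, complications related airway management, cardiologist and patient satisfactions". That is a claim about one arm against the other. The same paragraph places haemodynamics below the primary outcomes: "Our primary outcome measures were safety of airway management, and cardiologist and patient satisfactions", and then "Our study also recorded demographic characteristics, intraoperative and postoperative hemodynamics, level of hypoxemia, and duration of procedure as secondary outcome measures".

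Study Protocol describes the monitoring: "Standard monitoring procedures were used, including heart rate (HR), noninvasive blood pressure", with ECG and oxygen saturation. It gives no reading times and does not say that a pre-induction reading was recorded. The arms are independent, with 22 patients in Group 1 ("Forty two patients were randomly assigned to either the Group 1 (n=22, sedation and analgesia without any airway instrumentation") and 20 in Group 2.

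Statistical Analysis has three sentences that bear on continuous readings:

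- Between arms, normal data: "Differences between variables in two groups with normal distribution were compared with the paired t-test".
- Between arms, other data: "Continuous variables distributed abnormally were compared between the groups using a Mann–Whitney U test".
- Over time: "Differences between variables within the same group at different times were tested with the Friedman test", with Dunn pairwise comparisons where the result is significant.

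**The concern.** Friedman and Dunn ask whether readings changed over time in one arm. Neither asks whether the arms changed differently, so the only analysis that uses time cannot support the stabilisation claim.

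That leaves the two generic between-arm tests. They could be applied to haemodynamics, but nothing says to which variable, at which time, to raw values or change, with or without baseline, or to what measure of stability. Stabilisation itself is not defined. Two risks follow. The tests may be run at every reading time with no stated control of error, and the analyst is free to choose the comparison after seeing the data.

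**Working it through.** **Nothing to reproduce.** The documents contain no power, effect-size or variability figure for haemodynamics. The gap is shown by the text. The numbers below only indicate its size.

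**Inputs from the documents.** Arms of 22 and 20; significance level 0.05.

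**Assumed.** Two-sided tests; five normally distributed readings per patient (one before induction, four later); total SD 1; equal correlation ρ between any two readings, taken as 0.3, 0.5 and 0.7. Simulated results use 10,000 to 20,000 trials per setting.

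**1. A test at each later time.** With four independent tests, the chance of at least one false positive is 1 − 0.95⁴ = 18.5%. Readings on one patient are correlated, which lowers it. Simulated with Mann-Whitney U at each of the four times, it is about 17% at ρ = 0.3, falling to 13% at ρ = 0.7.

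**2. Only if within-arm results were set side by side.** If the Friedman test is significant with probability p₁ in one arm and p₂ in the other, exactly one is significant with probability p₁(1 − p₂) + p₂(1 − p₁). With an identical true change of 0.5 SD in both arms and ρ = 0.5, simulation gives p₁ = 0.501 and p₂ = 0.456, so 0.501 × 0.544 + 0.456 × 0.499 = 0.50. This is close to the worst case. At ρ = 0.5, for identical changes of 0, 0.3, 0.8 and 1.0 SD, the figures are 9%, 30%, 18% and 3%.

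**3. What a baseline-adjusted mean would do, and when it fails.** For the mean of m later readings adjusted for one earlier reading, the residual variance is (1 + (m − 1)ρ)/m − ρ². The standard error is its square root times √(1/22 + 1/20) = 0.309. At ρ = 0.5:

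| Readings averaged | Where the 0.7 SD effect is present | Difference in the mean | Residual SD | Difference / SE | Power |
|---|---|---|---|---|---|
| 4 | all 4 | 0.70 | √0.375 = 0.612 | 0.70/0.189 = 3.70 | about 95% |
| 4 | 2 of the 4 | 0.7 × 2/4 = 0.35 | 0.612 | 0.35/0.189 = 1.85 | about 43% |
| 2 | both | 0.70 | √0.5 = 0.707 | 0.70/0.218 = 3.20 | about 87% |

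Over ρ = 0.3 to 0.7, simulated power is 42-53% in the second row and 83-96% in the third. Without a baseline reading, the mean of four has SD √0.625 = 0.791. In the first-row setting that gives 0.70/0.244 = 2.87, or about 80% power.

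**4. The two meanings of stabilisation need different measures.** Power by simulation, four later readings, ρ = 0.3 to 0.7:

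| True difference between arms | ANCOVA of mean | Within-patient SD, Mann-Whitney U |
|---|---|---|
| Systematic drop of 0.8 v 0.3 SD | 71-83% | 5% |
| Within-patient scatter 1.5-fold higher in Group 1 | 5% | 79-80% |

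**The case against.** **Between-arm tests are present.** The plan compares continuous variables between groups, and haemodynamic readings are continuous. The ordinary reading is two-group tests between arms and Friedman within arms. This stands: a reader might infer that no between-arm analysis of haemodynamics was planned, and the text does not support that. What is missing is the target of the test.

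**No one says the within-arm results will be contrasted.** This also stands. A reader might infer that the sponsor meant to treat significance in one arm only as a group difference, with up to about a 50% error rate. The documents describe no such step, so that figure is conditional and secondary here.

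**Averaging is not always better.** The GLT is removed at the end of the procedure, while the outcome covers postoperative readings too. An effect confined to the procedure is plausible. Pooling all four readings would then give about 43% power at correlation 0.5, below the 57% for one reading taken while the effect is present. This stands and shapes the fix.

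**A mean level may not be stabilisation.** Correct. The definition must come before the method.

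**The misnamed paired t-test is the real error.** A paired test does not fit independent arms of 22 and 20, but that is a separate point. Renaming it would still leave stabilisation without a defined comparison.

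**Conclusion.** The concern holds as a gap in specification with a practical consequence. The plan makes a between-arm claim about stabilisation, its only time-based method cannot test that claim, and its two-group tests are not attached to any quantity that would. The most plausible harm is repeated testing: about a 13-17% chance of at least one false positive for one variable tested at four later times, rather than 5%.

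All the sizes rest on assumed reading times, correlations and normal data. The textual finding does not depend on them. The outcome is secondary, and the primary outcomes (airway safety, cardiologist and patient satisfaction) are unaffected. The sponsor should make the change, but the trial's main conclusions do not hang on it.

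**What to change.** 1. State whether stabilisation means a smaller systematic change or less fluctuation within a patient.
2. Make one between-arm comparison the inferential analysis for heart rate and for one named blood-pressure measure.
   - *Systematic change:* ANCOVA of each patient's mean of the intraoperative readings, from induction to the end of TEE, adjusted for the pre-induction reading. Report the group difference with its 95% CI. If no pre-induction reading was recorded, compare the unadjusted mean.
   - *Fluctuation:* within-patient SD of the same intraoperative readings, compared by Mann-Whitney U.
3. Summarise postoperative readings separately and do not pool them with the intraoperative ones.
4. Keep Friedman, Dunn and any per-time tests as descriptive, and do not read differing within-arm significance as a group difference.
5. The text is in the past tense, so label the measure post hoc if it was chosen after the data were seen.

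**Cost.** Slightly more analysis work, with no added patients or procedures. Two variables still mean two tests (1 − 0.95² = 9.8% if independent), so both should be reported. Each measure misses the other kind of instability. If no baseline reading exists, power for the mean falls (about 80% rather than 95% in the four-reading example).

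Suggested wording: *Haemodynamic stabilisation is defined as [smaller systematic change / less within-patient fluctuation] between induction and the end of TEE. It is compared between arms, for heart rate and [named blood-pressure measure], by [ANCOVA of the patient mean adjusted for the pre-induction reading / Mann-Whitney U on the within-patient SD]. All other haemodynamic tests are descriptive.*
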